DBS analysis for TDF drug levels has now been sufficiently validated such that concurrent plasma levels are not required (Castillo-Mancilla et al 2013). DBS cellular assays are still being validated and so whilst these tests will be done later, for the purposes of this proposal, the equivalent non-cellular assay will be done on the DBS in order to provide real time feedback to the randomised participants within the next monthly visit. The DBS will be from venous (as to capillary) blood which is currently validated.

We hypothesize that oral, daily PrEP (FTC/TDF) will be acceptable and used by HIV-negative adolescents, 15-19 years of age and in those who opt to use PrEP, PrEP adherence will be enhanced through client centered, motivational adherence counselling that includes feedback about blood drug levels.

The study will focus on adolescents in South Africa, where HIV prevalence among youth is high but involvement in HIV prevention clinical studies has been low. The study's outcomes will contribute to important prior and current research and will ultimately help build an innovative menu of prevention approaches for adolescents that allows for developmental variation and cultural

sensitivity.

Recent findings show both safety and efficacy of PrEP in adult populations (including men and transgender women who have sex with men; discordant heterosexual couples, and uninfected heterosexual men and women). [See section 2.6.5: Studies of Tenofovir and PrEP in Human Participants]. In addition, the iPrEx OLE study enrolled youth to receive PrEP and two adolescents studies, ATN 110 and 113 are currently enrolling young MSM aged 15-22 years in the USA.

Given the scarcity of data for PrEP and adolescents and as gaps in our knowledge persist, the integration of adolescents into HIV biomedical research is critical for the following reasons:

- Outcomes from research involving adolescents may strengthen capacity to create efficacious country-level health policies and prevention programmes that are truly responsive to the needs of this population.

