4.2 SUMMARY OF MAJOR ENDPOINTS

Primary endpoints:

Acceptability

- The proportion of participants who report willingness to use the study regimen, take up PrEP and remain on PrEP as part of a comprehensive prevention package.

- Assessment of acceptability as per questionnaire administered at study end.

Use

- Number of adolescents who continue to use PrEP (as indicated by DBS/ plasma levels) after the initial 3 month period
- The total time on PrEP for each adolescent (as indicated by DBS/plasma levels) and for the cohort as a whole in those individuals who indicated PrEP use by self report at the beginning of each 3 month period.

Safety

- Grades 2, 3, and 4 clinical and laboratory adverse events;

Secondary endpoints:

Adherence:

- Adherence to daily regimens of oral PrEP as evidenced by the use self-report, pill counts, and proportion of participants on FTC/TDF who have detectable drug levels. Proportion of blood samples with detectable drug levels
- Proportion of adolescents with detectable drug levels who report using PrEP
- Proportion of doses that are taken as instructed.

Sexual and other Behaviors

- Reported number of steady and casual sex partners, condom use (and change after introduction of study product), substance use prior to or during sex, as evidenced by participant responses to interviewer-administered questionnaires and focus groups.
- Proportion of scheduled HIV testing appointments missed, in relation to individual characteristics (age, sex, number of partners, use of other prevention methods) and the characteristics of the product.

HIV infection,

- as measured by seroconversion of study participants during the approximate 12 months of follow-up.

Exploratory endpoints:

Impact on adherence of providing information on drug (FTC/TDF) levels (as measured in Dried Blood Spot/Plasma) given as feedback during counseling sessions.

- Number of counselling opportunities in which drug level feedback is requested vs total number of counseling events
- Number and nature of participants who request drug level feedback.
- Correlation between self reported adherence and drug levels at each visit for each participant
- Correlation between self reported adherence and drug levels at each visit in the study overall.
- Proportion and number of participants whose adherence to study product improves when receiving the results of DBS/Plasma compared to those who do not receive feedback of results as measured by endpoints above.

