 - Proportion and number of participants who are tested using DBS and received results of DBS compared to participants who are tested using DBS but do not receive biofeedback of results.
 - Number of counselling opportunities in which drug level feedback is requested vs total number of counseling events
 - Number and nature of participants who request drug level feedback .
 - Correlation between self reported adherence and drug levels at each visit for each participant
 - Correlation between self reported adherence and drug levels at each

visit in the study overall.

- Proportion and number of participants whose adherence to study product improves when receiving the results of DBS compared to those who do not receive feedback of results as measured by endpoints above.

Consistent with the exploratory study objective to investigate the relationship between daily PrEP usage and sexual practices and behavior in adolescents, the following exploratory endpoints will be assessed

Sexual behaviour data obtained using questionnaires and a focus group.

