10.3 STUDY HYPOTHESIS

The DTHF protocol and research teams hypothesize that oral once daily PrEP (TDF/FTC) will be acceptable and utilized safely by healthy adolescents, between the ages of 15-19 years.

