Correlation of self reported adherence and presence of drug levels in participants who are tested using plasma drug levels or DBS and received results compared to participants who are tested using plasma/DBS but do not receive biofeedback of results.

Analysis:

These data will be described as proportions at each study visit; while we will calculate differences in proportions attending between participant who do and do not receive biofeedback results, no formal statistical tests will be used for this exploratory endpoint.

2.Exploratory: Sexual behaviour by coital diaries

Sexual behaviour data obtained using a questionnaires and focus group.

Analysis:

Data from questionnaires will be compared to self-reported sexual behaviour on a per participant and per visit basis. While this endpoint is exploratory, we anticipate using the distributions of the observed data to defined post-hoc boundaries of acceptable agreement, and then use this to estimate the proportion of participants with acceptable versus unacceptable agreement at each visit, and overall during the study.

Analysis of Focus Group data:

All focus groups and interviews will be transcribed and then analysed using Framework Analysis (Ritchie and Lewis; 2003). This approach was developed in the 1980's by researchers at the UK National Centre for Social Research and has been used extensively for applied or policy relevant qualitative research (Pope et al; 2000). It uses an analytical framework to organize data according to key themes, concepts and emergent categories in grids or matrices. This method facilitates both between case and within case analysis to look for patterns and connections. It provides a systematic, consistent and transparent approach to handling data that also enables analysis to go beyond description to interpretation where appropriate. In addition, it facilitates the linking of findings with

those of quantitative research, which will be relevant in comparing, contrasting and enhancing findings collected quantitatively in this study, in particular on PrEP acceptability and adherence. In addition, this triangulation of methods (qualitative and quantitative) has been advocated as an approach to increase the validity of findings (Mays and Pope; 2000, Shenton; 2004).

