participant. In analysis, we will first use graphical approaches to display the proportions of participants reporting binary sexual risk behaviours (or means of continuous measures) at each study visit over the 12-month period. Following this, we will use repeated measures methods (as described above) for both binary and continuous dependent variables, with PrEP access treated as a binary variable distinguishing visits in on vs. off PrEP phases; in the first instance, these models will not include other covariates.

2b. Proportion of scheduled HIV testing appointments that are missed, in relation to individual characteristics (age, sex, number of partners, use of other prevention methods) and the characteristics of the product.

Analysis:

“Missed appointments” will be defined as participants being >7 days late for a visit scheduled on a 28-day cycle. This measure will be analysed as a binary variable following the repeated measures approaches described above.

3. Secondary: HIV Incidence

HIV infection, as measured by seroconversion of study participants during the approximate 12 months of follow-up

Analysis:

The incidence of HIV will be described using person-time (rates per 100 person years of observation) and product-limit (survival proportion) approaches. For both methods, the date of seroconversion will be the midpoint of the interval between the last negative and first positive HIV test. For participants lost to follow-up, the date of censoring will be one day after the last visit attended.

C. Exploratory Endpoints:

1. Exploratory: Dried Blood Spot/plasma biofeedback

Correlation of self reported adherence and presence of drug levels in participants who are tested using plasma drug levels or DBS and received results compared to participants who are tested using plasma/DBS but do not receive biofeedback of results.

CHAMPS: Choices For Adolescent Prevention Methods for SOUTH AFRICA

Pilot study B: “PlusPills”

A Demonstration Open Label Study to Assess the Acceptability and Use of Truvada Pre-exposure Prophylaxis in Healthy, HIV-Uninfected Adolescents, 15-19 Years of Age.

Analysis:

These data will be described as proportions at each study visit; while we will calculate differences in proportions attending between participant who do and do not receive biofeedback results, no formal statistical tests will be used for this exploratory endpoint.

2.Exploratory: Sexual behaviour by coital diaries

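### The only feedback versus no-feedback difference in analysis C.1 is in attendance, and the endpoint that adherence improves with feedback has no defined measure or contrast

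*Protocol*

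**What the plan says.** Protocol section 2.5 hypothesises that, in those who opt for PrEP, "PrEP adherence will be enhanced through client centered, motivational adherence counselling that includes feedback about blood drug levels". Section 4.1 lists adherence by choice of biofeedback among the things the study evaluates. The matching exploratory endpoint appears in the Protocol Summary, in sections 4.2 and 10.2, and in the SAP endpoint list. In section 10.2 it begins "Proportion and number of participants whose adherence to study product improves when receiving the results of DBS compared to those who do not receive", and its measure is given only by reference to the endpoints listed before it.

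The analysis is in section 10.6, C.1. It names its data as "Correlation of self reported adherence and presence of drug levels in participants who are tested using plasma drug levels or DBS and received results", set against participants who were tested but not given results. It continues: "These data will be described as proportions at each study visit". The between-group step follows: "we will calculate differences in proportions attending between participant who do and do not receive biofeedback results". C.1 of the SAP has the same step: "differences in proportions attending between participant who do and do not receive". Both documents state that no formal test will be done for this endpoint.

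The adherence analysis (section 10.6, B.1, and the same item in the SAP) defines perfect and effective adherence at each visit. It sets subgroups by age, gender and sexual activity, and plans exploratory repeated-measures models of predictors of adherence. Feedback is not named as a subgroup or as a predictor.

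**The concern.** An analyst who follows C.1 as written would compute a difference in attendance. That is neither the subject of C.1 nor the improvement endpoint. In this plan attendance belongs to a separate secondary item, missed HIV testing appointments (section 10.6, B.2b).

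At stake is whether the study can say anything planned about feedback and adherence. If the outcome, the comparison visit and the meaning of *improves* are settled only once data are in hand, the definition is chosen post hoc. An attendance difference could also be presented as evidence about feedback when it says nothing about pill-taking.

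**Working it through.** The point is textual, so the check traces hypothesis, endpoint and analysis through both documents.

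1. **Hypothesis.** Section 2.5: feedback-based counselling will raise adherence. The outcome needed is adherence, by feedback status.
2. **Endpoint.** Sections 4.2 and 10.2 and the SAP list: participants whose adherence improves with feedback versus without. This needs a measure, a starting visit, a later visit and a rule for improvement. The text points back to earlier endpoints without choosing one, and gives none of the other three.
3. **C.1, description.** Self-report against presence of drug, as proportions per visit, by feedback status. Agreement between the two is a property of reporting: a participant who takes no pills and says so agrees perfectly. The agreement proportion can therefore rise or fall without any change in adherence.
4. **C.1, contrast.** A difference in the proportion *attending*. This matches neither step 2 nor step 3.
5. **B.1.** It supplies usable per-visit definitions and a repeated-measures model. Its covariates are given as examples and feedback is not among them, so a feedback term is possible but not planned.

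**What attendance could show depends on the reading.** If it means attendance at the visit where feedback is offered, among those offered it, both groups are at 100% and the difference is 0. If participants who missed the visit count as not receiving feedback, the difference favours feedback by construction. If it means attendance at the next visit, it can take any value. C.1 does not say which is meant, and on no reading is it adherence.

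**The plan's own figure.** The only sample-size figure is for acceptability: 135 / (1 − 0.10) = 150, which reproduces the stated enrolment. No figure is given for the feedback comparison, so none changes.

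**Precision of a corrected contrast (illustration).** The documents give no feedback uptake and no adherence rate. Assume 50% to 85% choose feedback, a common adherence proportion p of 30% to 50%, one visit, and independent participants. The half-width is 1.96 × √[p(1 − p)(1/n₁ + 1/n₂)].

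- 135 on PrEP: 68 v 67 at p = 0.30 gives 1.96 × √(0.21 × 0.02963) = 15.5 points; 115 v 20 at p = 0.50 gives 1.96 × √(0.25 × 0.05870) = 23.7 points.
- 100 on PrEP: 18.0 (50 v 50, p = 0.30) to 27.4 (85 v 15, p = 0.50).
- 70 on PrEP: 21.5 (35 v 35, p = 0.30) to 33.5 (60 v 10, p = 0.50).

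The corrected contrast would be descriptive and imprecise at any single visit, which suits its exploratory status.

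**Are the data planned?** The feedback decision is recorded at each follow-up visit (Protocol Summary, Design; section 4.1). Drug levels are scheduled at weeks 4, 8, 12, 24, 36 and 48. The later samples depend on PrEP use: from week 36 in section 7.8, from week 24 in the schedule of visits table. A participant who stops before the next visit may therefore have no drug level there.

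**The case against.** The strongest reply is that C.1 should be read as a whole. It opens with self-reported adherence and drug levels and says those data will be described by visit, so *attending* looks like a one-word slip. B.1 gives adherence metrics and exploratory predictor models that do not exclude feedback. The second focus groups ask about the impact of drug-level feedback. The item is exploratory, the absence of a test is declared, and the statistical hypothesis in section 10.3 is only that "oral once daily PrEP (TDF/FTC) will be acceptable and utilized safely by healthy adolescents".

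Most of this stands, and it rules out some stronger readings. A reader might infer that attendance replaces adherence altogether, or that the feedback hypothesis is never analysed. The documents do not support that: a per-visit description of adherence and drug level by feedback status is planned. A reader might also infer that the attendance difference must be 0. That holds only on a same-visit reading which the text does not state.

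Two things do not stand. The slip is an inference, and the same word is the operative instruction in both documents. Correcting it would also leave the improvement endpoint without a starting visit, a rule or a feedback contrast. A model that could include feedback is not a plan to include it.

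**Conclusion.** The point holds in a limited form. The only specified difference between feedback groups is on the wrong outcome, and the improvement endpoint cannot be computed from the text. The planned description of self-report against drug level informs reporting accuracy, so the section 2.5 hypothesis is not directly addressed.

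The consequence is confined to an exploratory objective. The primary and secondary endpoints, the sample size and the section 10.3 hypothesis are unaffected, and the absence of a formal test is not a fault here. The half-widths above rest on assumed uptake and adherence, and only indicate how coarse a corrected estimate would be. Participants choose feedback afresh at each session (section 6.4), so even a corrected difference would be an association and not an effect of feedback.

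**What to change.** In C.1 of both documents:

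- **Contrast.** Replace the attendance difference with the difference, with 95% CI and no formal test, in the proportion meeting the B.1 effective-adherence definition at the next scheduled visit, by whether feedback was received at the current visit. Include drug level among the measures and report each measure separately. B.1 refers to therapeutic levels without a number, so state the threshold before analysis.
- **Improvement.** Define it as change in adherence status from the current visit to the next. State the denominator, since a participant already classed as adherent cannot improve on a binary measure.
- **Repeated choices.** Use the repeated-measures model planned in B.1, with feedback as a visit-varying covariate, adjustment for current-visit adherence, and participant as the unit of clustering.
- **Stopping PrEP.** State how participants who stop before the next visit, and so may have no drug level, are counted. Reconcile section 7.8 with the schedule table on which samples depend on PrEP use.
- **Agreement.** Keep self-report against drug level as a separate summary of reporting accuracy.
- **Interpretation.** Label all results as associations.

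The cost is wording in the Protocol and SAP. It needs no new visits, samples or participants.

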3.3 EXPLORATORY OBJECTIVES

- To explore the utility of Dried Blood Spot (DBS)/Plasma drug levels and the impact of biofeedback of results as an adherence enhancing strategy among HIV-negative adolescents between 15 and 19 years of age
- To explore the relationship between daily PrEP usage and sexual practices and behavior in adolescents.

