Sexual behaviour data obtained using a questionnaires and focus group.

Analysis:

Data from questionnaires will be compared to self-reported sexual behaviour on a per participant and per visit basis. While this endpoint is exploratory, we anticipate using the distributions of the observed data to defined post-hoc boundaries of acceptable agreement, and then use this to estimate the proportion of participants with acceptable versus unacceptable agreement at each visit, and overall during the study.

Analysis of Focus Group data:

All focus groups and interviews will be transcribed and then analysed using Framework Analysis (Ritchie and Lewis; 2003). This approach was developed in the 1980's by researchers at the UK National Centre for Social Research and has been used extensively for applied or policy relevant qualitative research (Pope et al; 2000). It uses an analytical framework to organize data according to key themes, concepts and emergent categories in grids or matrices. This method facilitates both between case and within case analysis to look for patterns and connections. It provides a systematic, consistent and transparent approach to handling data that also enables analysis to go beyond description to interpretation where appropriate. In addition, it facilitates the linking of findings with those of quantitative research, which will be relevant in comparing, contrasting and enhancing findings collected quantitatively in this study, in particular on PrEP acceptability and adherence. In addition, this triangulation of methods (qualitative and quantitative) has been advocated as an approach to increase the validity of findings (Mays and Pope; 2000, Shenton; 2004).

CHAMPS: Choices For Adolescent Prevention Methods for SOUTH AFRICA

Pilot study B: “PlusPills”

A Demonstration Open Label Study to Assess the Acceptability and Use of Truvada Pre-exposure Prophylaxis in Healthy, HIV-Uninfected Adolescents, 15-19 Years of Age.

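### Exploratory item C.2 names coital diaries that are not scheduled, leaves its comparator undefined and omits PrEP use, so it cannot address its own objective

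*Protocol*

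**What the plan says.** Protocol 3.3 sets the exploratory objective: "To explore the relationship between daily PrEP usage and sexual practices and behavior in adolescents". Protocol 10.2 attaches this endpoint to it: "Sexual behaviour data obtained using questionnaires and a focus group".

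The matching analysis is item C.2 of Protocol 10.6. Its heading is "2.Exploratory: Sexual behaviour by coital diaries", but the line below gives the data as "Sexual behaviour data obtained using a questionnaires and focus group". The analysis is then: "Data from questionnaires will be compared to self-reported sexual behaviour on a per participant and per visit basis". The plan anticipates "using the distributions of the observed data to defined post-hoc boundaries of acceptable agreement", which will serve to "estimate the proportion of participants with acceptable versus unacceptable agreement at each visit, and overall during the study".

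The SAP carries the same item under the same heading, "Exploratory: Sexual behaviour by coital diaries", with no further detail.

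**The concern.** Three things do not fit. The heading names an instrument that the data line beneath it does not. The comparison sets questionnaire data against self-reported behaviour, although the questionnaire is itself self-report and no other source is named. The output is a proportion in agreement, which describes how well two measures of behaviour match, whereas the objective asks how behaviour varies with PrEP use.

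At stake is whether this objective gets an analysis that can be programmed and interpreted. As written, an analyst would have to invent the comparator, choose the limits after seeing the data, and report a figure that says nothing about PrEP.

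**Working it through.** The plan gives no figure here to reproduce. The check traces data sources and sets the passages side by side.

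**1. Is a diary collected?** The objectives (3.3), endpoints (Summary, 4.2, 10.2), visit procedures (7.1 to 7.6), behavioural evaluations (7.9) and visit schedule (the table following 7.12) contain no diary. The only mention is the C.2 heading, in each document.

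**2. What could the second source be?** C.2 needs data per participant and per visit.

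| Candidate | Per participant, per visit? | Named as analysis data for C.2? |
|---|---|---|
| Sexual risk behaviour questionnaire (enrolment, weeks 4, 8, 12, 24, 36, 48, 52: 8 administrations) | Yes | Yes, as the questionnaire side |
| End-of-study focus groups (4.1) | No: 2 groups × 2 sites × 6–8 people = 24–32 of 150 (16–21%), once, in the last four weeks | Named as endpoint data, but unusable for this comparison |
| Counselling risk assessment (16.8) | Yes, reassessed at each visit | No |
| Coital diary | Not scheduled | Heading only |

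No candidate is both usable and designated. The comparator is therefore undefined.

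**3. What do post-hoc limits do?** Let d be the difference between two measures and c the limit. The share called acceptable is the number with |d| ≤ c divided by the number compared. It never falls as c rises, and it equals 1 once c reaches the largest observed |d|. If c is placed at the q-quantile of the observed |d|, the pooled share is about q. The overall level would then reflect the choice of c; only variation between visits or participants would carry information.

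**4. Does PrEP use enter?** No term in C.2 refers to it. This does not depend on the missing diary: with a real diary, agreement between two behaviour measures would still be instrument validation and not an association with PrEP.

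**5. How far does secondary analysis 2a fill the gap?** It takes partner number, casual partners, substance use before sex and condom use at each visit, and fits repeated-measures models with a binary on/off PrEP phase. Three gaps remain.

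- The exposure is access by phase. Protocol 2.5 and 2.6.7 warn that reported use can be false, and drug levels are collected, but 2a does not use them.
- The first models have no covariates, and phase is tied to time. Protocol 10.6 takes use in the first 3 months as 100% for all 150 participants. Of the 8 questionnaire visits, enrolment precedes PrEP for everyone (1) and weeks 4, 8 and 12 are on PrEP for everyone (3). On and off participants clearly coexist only at weeks 24, 36 and 48 (3). Week 52 (1) is unclear: Section 7.4 and the visit table supply no product at week 48, while Section 7.6 places routine withdrawal at week 52. The sum is 1 + 3 + 3 + 1 = 8. Without adjustment for visit, the on/off contrast mixes PrEP with time on study.
- C.2 does not refer to 2a, so the plan does not tell the reader that 2a is meant to serve this objective.

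**6. Are drug levels available throughout?** No. The visit table schedules them for all at weeks 4, 8 and 12 and marks weeks 24 to 52 as on PrEP only. Section 7.8 restricts weeks 36 to 52 in the same way, and Section 7.6 exempts those who have discontinued. A drug-level exposure therefore exists only for sampled intervals.

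**The case against.** The strongest reply is that the question is already analysed. Analysis 2a takes change in sexual risk with PrEP as its key question, over nearly the same outcomes. The end-of-study focus groups are drawn separately from adherent PrEP choosers and from non-choosers or poor adherers, and are asked about risk compensation and condom use. Framework Analysis then links their answers to the quantitative results. This stands. A reader might infer that the objective is never analysed against PrEP use, and the documents do not support that. What remains is that 2a covers it in part, for the reasons in step 5, and that C.2 itself does not.

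The second reply concerns the comparator. A reader might infer that the questionnaire is compared with itself, so that agreement is 100% by construction. The documents do not establish this. The counselling assessment in Protocol 16.8 is another individual-level report of sexual activity, partners, substance use and condom use at each visit, and the plan may have had it in mind. The supportable statement is that the second source is not named.

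Thirdly, the item is exploratory, and the plan is open about setting limits post hoc. That limits the consequence. It does not make the comparison executable or bring PrEP use into it.

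**Conclusion.** The point holds in limited form. Item C.2, in both documents, has a heading for an instrument that is not scheduled, an undefined comparator, limits drawn from the data they are applied to, and no PrEP term. It cannot address the objective in Protocol 3.3 and 10.2. That objective is covered partly by 2a and, qualitatively, by the focus groups.

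The size is modest: one exploratory item, with no primary or secondary conclusion affected and no numerical error. It is still worth correcting, because the item would otherwise be improvised or dropped.

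Two assumptions apply. The absence of a diary is established from the public text, which includes the whole visit schedule; a few pages and the questionnaires themselves are not in it. The count of visits in step 5 assumes that participants follow the planned first 3 months; early stops or holds would create some off-PrEP time before week 12.

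**What to change.** In Protocol 10.6 and the SAP, delete the diary heading and the agreement analysis in C.2. Replace them with an exploratory extension of 2a:

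- **Outcomes:** partner numbers, condom use and substance use around sex, at each follow-up questionnaire (up to 7 after enrolment).
- **Exposure, all participants:** PrEP use in the same interval, from the recorded choice to continue, stop or restart, or from self-report.
- **Exposure, sampled intervals only:** drug level, with the restriction after week 12 to those on PrEP stated beside the result.
- **Model:** repeated measures clustered by participant, adjusted for visit and the enrolment value of the outcome. State the recall period of the questionnaire so that exposure and outcome cover the same interval.
- **Cross-reference:** say that 2a and the focus-group analysis also bear on this objective.

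If a diary was truly intended, the alternative is to add it to Section 7 and the visit table, name both sources, fix the limits in advance and label the analysis as measurement validation. The objective would still need the PrEP analysis above.

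The cost is a wording change in two documents and a little extra analysis on data mostly already scheduled. The drug-level version will not cover all off-PrEP time, and results remain exploratory.
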